#### **6.5.4. Psychiatric Evaluation**

Treatment with apremilast is associated with an increase in adverse reactions of depression. Before using apremilast in subjects with a history of depression and/or suicidal thoughts or behavior, the investigator should carefully weigh the risks and benefits of treatment with apremilast in such patients. Subjects should be advised of the need to be alert for the emergence or worsening of depression, suicidal thoughts or other mood changes, and if such changes occur to contact the Investigator.

If a patient suffers from new or worsening psychiatric symptoms, or suicidal ideation or suicidal attempt is identified, it is recommended to discontinue study treatment (see Section 11).

#### **6.5.5. Diarrhea, Nausea and Vomiting**

Apremilast has been associated with AE reports of diarrhea in clinical trials. Most diarrhea events were of mild or moderate severity and reported within the first 2 weeks of treatment, usually resolving within 4 weeks without medical intervention.

Diarrhea is the passage of three or more loose or liquid stools per day, or more frequently than is normal for the individual (World Health Organization [WHO], 2013). Following the definition of diarrhea by the WHO and taking a more conservative approach, the AE of diarrhea in this protocol is defined as having two or more watery/liquid stools in a day.

To better characterize diarrhea and to distinguish similar events coding to the Medical Dictionary of Regulatory Activities (MedDRA) preferred term of diarrhea, subjects reporting diarrhea or similar events (eg, frequent bowel movements, loose bowels, etc.) will be asked whether they have had two or more watery/liquid stools in a day. Subjects who respond “yes” to this question will be further asked how often, on average, have they experienced two or more watery/liquid stools in a day. Subjects who respond “no” to the question will not be asked any further questions.

There have been post-marketing reports of severe diarrhea, nausea and vomiting associated with the use of apremilast. Most events occurred within the first few weeks of treatment. In some cases, patients were hospitalized.

Subjects 65 years of age or older and those taking medications that can lead to volume depletion or hypotension may be at a higher risk of complications. Subjects should be monitored for the occurrence of severe diarrhea, nausea and vomiting. If subjects develop severe diarrhea, nausea and vomiting, discontinuation of treatment with study treatment may be necessary (see Section 11).

#### **6.5.6. Tuberculosis**

After an extensive clinical development program, there is no current evidence that apremilast has the potential to activate latent TB. Therefore, no TB testing will be done in this protocol. Investigators can test for TB if clinically indicated, using the site’s local or country specific guidelines. If the subject has active or latent TB, he/she should be treated according to local guidelines. Subjects who require TB treatment at any time during the study must be discontinued.

#### **6.5.7. Clinical Laboratory Evaluations**

Clinical laboratory evaluations will be performed by the central laboratory, and as indicated in Section 5. Clinical laboratory evaluations include: RF, CBC (RBC count, hemoglobin, hematocrit, WBC count and differential, absolute WBC counts, platelet count); serum chemistries (total protein, albumin, calcium, phosphorous, glucose, triglycerides, total cholesterol [TC], total and direct bilirubin, alkaline phosphatase, AST, ALT], sodium, potassium, chloride, bicarbonate [carbon dioxide, CO2], BUN, creatinine, creatinine clearance, lactate dehydrogenase [LDH], and magnesium); [REDACTED]; hemoglobin A1c (HbA1c); and urinalysis (specific gravity, pH, glucose, ketones, protein, blood, bilirubin, leukocyte esterase, nitrite, and urobilinogen). Urinalysis will be performed by the central laboratory; microscopic urinalysis (epithelial cells, RBC, WBC, and casts) will be performed only if the urinalysis is abnormal.

#### **6.5.8. Adverse Events**

All subjects will be monitored for adverse events (AEs) during the study. Assessments may include monitoring of any or all the following parameters: the subject’s clinical symptoms, laboratory, pathological, radiological, or surgical findings; physical examination findings; or other appropriate tests and procedures.

[figure not shown]
All AEs will be recorded by the investigator from the time the subject signs informed consent to 28 days after the last dose of IP. AEs and SAEs will be recorded on the AE page of the case report form (CRF), the paper SAE reporting form (SAEs) and in the subject’s source documents.

All SAEs must be reported to Amgen Global Patient Safety within 24 hours of the investigator's knowledge of the event using the paper Serious Adverse Event Report Form by facsimile/email or the paper SAE Report Form directly to Amgen Global Patient Safety

Details of AE/SAE reporting can be found in Section [10](#) of the protocol.

It should be noted that worsening of a subject's PsA should be considered as worsening of disease under study and should not be captured as an adverse event.

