- Low-potency topical glucocorticoids (or locally available equivalent) as background therapy for treatment of psoriasis on the face, axillae and groin in accordance with the manufacturers' suggested usage during the course of the study.
- Coal tar shampoo and/or salicylic acid scalp preparations on scalp psoriasis lesions.
- A nonmedicated skin emollient (eg, Eucerin® cream) for body psoriasis lesions only.

Medications for conditions other than PsA and psoriasis, which are not prohibited in Section 8.2, are permitted and must be recorded in the subject's source documents and as a concomitant medication on the CRF.

The following therapy will be permitted after the Week 24 Visit for subjects with worsening arthritic symptoms of PsA:

- Change of NSAID type and/or dose
- Administration of no more than 40 mg intramuscular (IM) or intra-articular (IA) glucocorticoid (triamcinolone hexacetonide or equivalent) at a single visit, up to Week 36, not to exceed two glucocorticoid IM and/or IA administrations in any 6 month-interval. Injected joints should not be counted during the visits that will take place within 4 weeks of the intra-articular injection.
- Short course ( $\leq 2$  weeks) of low-dose oral glucocorticoids (prednisone  $\leq 10$  mg/day or equivalent), to be completed up to Week 36 and not to exceed one course in a 6-month interval

In order to minimize the impact on ongoing efficacy assessments, the investigator should use the least intensive regimen to ameliorate the subject's worsening PsA symptoms. After Week 24, if subjects experience a decrease in PsA clinical disease activity, the investigator may opt to taper the background treatment; however, only one agent may be reduced or tapered at any one time. After the first agent's taper has been completed (not required to be zero), the dose must be stable for at least 4 weeks prior to starting the taper of the next agent. Subjects are recommended to have a reduction of background therapy in the following order: first MTX, second glucocorticoids and third NSAIDs or other pain medication. If clinically indicated, the investigator may opt to reduce the medications in a different order. Any further questions/concerns regarding dose reductions can be discussed with the Sponsor.

All other prohibited medications listed in Section 4.4 (Exclusion Criteria) and Section 8.2 (Prohibited Concomitant Medications and Procedures) remain in effect through the end of the subject's participation in the study.

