## 10. ADVERSE EVENTS

### 10.1. Monitoring, Recording, and Reporting of Adverse Events

An AE is any noxious, unintended, or untoward medical occurrence that may appear or worsen in a subject during the course of a study. It may be a new intercurrent illness, a worsening concomitant illness, an injury, or any concomitant impairment of the subject's health, including laboratory test values (as specified by the criteria in Section 10.3), regardless of etiology. Any worsening (ie, any clinically significant adverse change in the frequency or intensity of a pre-existing condition) should be considered an AE. A diagnosis or syndrome should be recorded on the AE/SAE page of the CRF rather than the individual signs or symptoms of the diagnosis or syndrome.

Abuse, withdrawal, sensitivity or toxicity to apremilast should be reported as an AE. Overdose, accidental or intentional, whether or not it is associated with an AE, should be reported on the overdose CRF. (See Section 7.2.1 for the definition of overdose.) Any sequela of an accidental or intentional overdose of an IP which meets the definition of an adverse event should be reported as an AE on the CRF. If the sequelae of an overdose meet serious criteria, then it must be marked as serious on the CRF and the paper SAE Report form. The overdose itself should not be reported as an AE.

In the event of overdose, the subject should be monitored as appropriate and should receive supportive measures as necessary. There is no known specific antidote for apremilast overdose. Actual treatment should depend on the severity of the clinical situation and the judgment and experience of the treating physician.

All subjects will be monitored for AEs during the study. Assessments may include monitoring of any or all of the following parameters: the subject's clinical symptoms, laboratory, pathological, radiological or surgical findings, physical examination findings, or findings from other tests and/or procedures.

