### 10.2.1. Seriousness

An SAE is any AE occurring at any dose that:

- Results in death;
- Is life-threatening (ie, in the opinion of the Investigator, the subject is at immediate risk of death from the AE);
- Requires inpatient hospitalization or prolongation of existing hospitalization (hospitalization is defined as an inpatient admission, regardless of length of stay);
- Results in persistent or significant disability/incapacity (a substantial disruption of the subject's ability to conduct normal life functions);
- Is a congenital anomaly/birth defect;
- Constitutes an important medical event.

Important medical events are defined as those occurrences that may not be immediately life-threatening or result in death, hospitalization, or disability, but may jeopardize the subject or require medical or surgical intervention to prevent one of the other outcomes listed above. Medical and scientific judgment should be exercised in deciding whether such an AE should be considered serious.

Events **not considered** to be SAEs are hospitalizations for:

- a standard procedure for protocol therapy administration. However, hospitalization or prolonged hospitalization for a complication of therapy administration will be reported as an SAE.
- routine treatment or monitoring of the studied indication not associated with any deterioration in condition.
- the administration of blood or platelet transfusion as routine treatment of studied indication. However, hospitalization or prolonged hospitalization for a complication of such transfusion remains a reportable SAE.
- a procedure for protocol/disease-related investigations (eg, surgery, scans, endoscopy, sampling for laboratory tests, bone marrow sampling). However, hospitalization or prolonged hospitalization for a complication of such procedures remains a reportable SAE.
- hospitalization or prolongation of hospitalization for technical, practical, or social reasons, in absence of an AE.
- a procedure that is planned (ie, planned prior to start of treatment on study); must be documented in the source document and the CRF. Hospitalization or prolonged hospitalization for a complication remains a reportable SAE.

Approved

- an elective treatment of or an elective procedure for a pre-existing condition, unrelated to the studied indication, that has not worsened from baseline.
- emergency outpatient treatment or observation that does not result in admission, unless fulfilling other seriousness criteria above.

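### Protocol 6.5.8 excludes worsening of PsA from adverse event capture without excepting serious worsening, while 10.1, 10.2.1 and 10.5 lead to a 24-hour SAE report for the same event; no precedence is stated.

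*Protocol*

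**What the plan says.** Four parts of the protocol and one of the SAP bear on this.

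- **Protocol 6.5.8 (Adverse Events)** closes by saying that worsening of a subject's PsA "should be considered as worsening of disease under study and should not be captured as an adverse event". Seriousness is not mentioned. Just before this the section states: "Details of AE/SAE reporting can be found in Section" 10.
- **Protocol 10.1** defines worsening in general terms: "any clinically significant adverse change in the frequency or intensity of a pre-existing condition) should be considered an AE". The disease under study is neither named nor excluded.
- **Protocol 10.2.1** builds seriousness on that definition: "An SAE is any AE occurring at any dose that" meets a listed criterion. One criterion is "Requires inpatient hospitalization or prolongation of existing hospitalization"; another is persistent or significant disability. Among hospitalisations not counted as SAEs are those for "routine treatment or monitoring of the studied indication not associated with any deterioration in condition".
- **Protocol 10.5** requires an AE meeting any seriousness criterion to be reported as an SAE within 24 hours, with no exception for PsA.
- **SAP 4.2.5.1** defines a TEAE from the recorded AEs by timing relative to dosing. It has no rule for worsening of PsA.

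**The concern.** Keeping ordinary disease fluctuation out of the AE tables is a common and reasonable choice when efficacy assessments already record it. The difficulty is that the exclusion in 6.5.8 has no limit. Because an SAE must first be an AE, an event that 6.5.8 removes from AE capture cannot become an SAE, however serious it is. Section 10, to which 6.5.8 refers the reader, points the other way for the same event.

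At stake is the handling of a small but important class of events: PsA worsening that leads to admission or lasting disability. The section a site follows decides whether such an event reaches the sponsor's safety group within 24 hours, is followed to resolution under 10.2.6, is assessed for expectedness under 10.6 if suspected to be drug-related, and appears in the TEAE and serious TEAE tables (SAP 12.1). Safety and tolerability is a secondary objective. With a single arm, no concurrent comparison would reveal uneven recording between sites.

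**Working it through.** No arithmetic applies, and the plan gives no figure to reproduce. The check is to take one event, an inpatient admission because a subject's PsA has worsened, through each rule.

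**Route A, Protocol 6.5.8.**
1. The event is worsening of PsA, so it is not captured as an AE.
2. Section 10.2.1 requires an SAE to be an AE first, so it is not an SAE.
3. The 24-hour duty in 10.5 applies to AEs, so nothing is reported.

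**Route B, Protocol 10.1, 10.2.1 and 10.5.**
1. PsA is pre-existing in every subject: inclusion criterion 5 requires a diagnosis of at least 3 months. A worsening that leads to admission would ordinarily be clinically significant, so under 10.1 it is an AE.
2. Inpatient admission is a seriousness criterion in 10.2.1, so it is an SAE unless an exemption applies.
3. The exemption for the studied indication covers routine treatment or monitoring without deterioration. This event is a deterioration, so the exemption does not cover it.
4. The other exemptions cover therapy administration, transfusion, disease-related investigations, technical or social reasons, planned procedures, elective care for unrelated conditions, and outpatient emergency care. None covers an admission because PsA has worsened.
5. Under 10.5 the event is reported within 24 hours.

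**Comparison.** The same event is omitted under A and reported as an SAE under B. A worsening that causes persistent disability splits in the same way, through the disability criterion.

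**Does anything settle the order?** Neither document says which section prevails. The Table of Events (footnote e) sends sites to 6.5.8 for adverse events, and 6.5.8 sends them on to Section 10. A site that stops at 6.5.8 follows A; one that continues can follow B.

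**Can the analysis repair it?** SAP 4.2.5.1 works only on events already recorded as AEs, so the split passes unchanged into the TEAE and serious TEAE summaries.

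**The case against.** The strongest reply is that 6.5.8 is a specific carve-out from a general definition. Section 10.1 never names PsA; 6.5.8 does, directly after pointing to Section 10. On that reading the sections are compatible and ordinary flares are plainly excluded. This stands for non-serious worsening. It does not settle serious worsening: no precedence is stated, the deterioration condition in 10.2.1 would have little purpose for PsA if its deterioration could not be an AE, and if the carve-out did prevail, a hospitalised flare could not reach SAE reporting at all.

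It is also fair that 10.2.1 only implies that admission with deterioration is reportable. That exemption is not the only one: "a procedure for protocol/disease-related investigations" is exempt with no deterioration condition, so an admission purely for investigation could be left out under either route.

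Several stronger inferences should not be drawn:

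- *That the safety count is off by a known amount.* Table 10 gives SAEs in 47 of 721 subjects in the first 52 weeks of earlier trials (6.5%; 0.065 × 120 = 7.8 subjects here). A reader might add an assumed number of serious flares to that. The text available to me contains no such rate (the body of Table 9 was not in it), and it does not show whether the earlier trials already counted serious flares as SAEs. Any percentage would be the assumption restated.
- *That withdrawals for worsening PsA go uncounted.* Lack of efficacy is a separate discontinuation reason in Protocol 11.1 and SAP section 8.
- *That background tapering makes serious flares likely.* Section 8.1 says "the investigator may opt to taper the background treatment" after Week 24, but only when clinical disease activity has decreased and one agent at a time. Nothing there links tapering to admissions.
- *That worsening disappears from the data.* Joint counts, global assessments and pain are recorded at every treatment visit, and concurrent medications and procedures throughout. What is at risk is classification and expedited reporting.

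**Conclusion.** The concern holds for PsA worsening that meets a seriousness criterion. For that class, the current protocol supports both omission and a 24-hour SAE report, and the SAP carries forward whatever the site did. This rests on the wording alone, with two assumptions: that worsening leading to admission or lasting disability is clinically significant in the sense of 10.1, and that the deterioration condition in 10.2.1 means what it implies.

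The effect on SAE counts cannot be estimated from the text available, and the number of events may be very small. The MRI primary endpoint and the efficacy analyses are not touched. A reader might infer that 10.1 flatly contradicts 6.5.8 for every flare. The documents do not support that, because the carve-out reading is adequate for non-serious worsening. The point still merits correction, because it concerns SAE reporting and events that were never recorded are hard to recover after database lock.

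**What to change.** Reconcile 6.5.8 with 10.1 and 10.2.1 by limiting the exclusion. In substance: worsening of PsA that meets no seriousness criterion in 10.2.1 is not recorded as an AE; worsening of PsA that meets any of those criteria is recorded as an AE and reported as an SAE under 10.5. Put the same sentence in 10.1 so that a site reaches the same answer from either section. The SAP's TEAE definition can then stay as it is.

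Before database lock, ask sites to check hospitalisations in source documents against the clarified rule and to enter any event that was left out.

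The cost is a protocol amendment, which under Protocol 13.5 needs written IRB/EC approval before implementation unless it is administrative (a changed SAE rule is hard to call that), together with a site memo, the source check, and possibly a slightly higher SAE count. Non-serious flares remain outside the AE tables, as 6.5.8 provides.

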## 6.6. Biomarkers

[figure not shown]

## 6.7. Subject-reported Outcomes

The following assessments will be conducted as outlined in the Table of Events, Section [5](#).

### 6.7.1. Psoriatic Arthritis Impact of Disease 12-domain Questionnaire (PsAID-12)

The PsAID is a validated score reflecting the impact of disease in PsA. The PsAID-12 is a 12-item, self-administered questionnaire that reflects the impact of PsA from the perspective of the patient. It is composed of 12 physical and psychological domains. Each domain is rated from 0 to 10 with a different weighting. The total score is divided by 20. The final score has a range from 0 (best status) to 10 (worst status) with a cut-off of 4 ([Appendix K; Gossec, 2014](#)).

Approved

## 7. DESCRIPTION OF STUDY TREATMENTS

### 7.1. Description of Investigational Product(s)

The chemical name of apremilast (CC-10004) is N-[2-[(1S)-1-(3-ethoxy-4-methoxyphenyl)-2-(methylsulfonyl)ethyl]-2,3-dihydro-1,3-dioxo-1H-isoindol-4-yl] acetamide.

Apremilast will be provided by Amgen Inc. and labelled appropriately as IP for this study.

Apremilast will be provided as 10, 20, or 30 mg tablets in blister cards for dose titration purposes. Apremilast will also be provided as 30 mg tablets in high-density polyethylene (HDPE) bottles (approximately 80 tablets) with child-resistant caps. The apremilast dosing schedule and dose adjustments to be followed for this study are described in Section 7.2. Please refer to the IB for more details on approved indications, known precautions, warnings, and adverse reactions of apremilast.

Additional information may be included on the label as needed or applicable. Label(s) for IP will contain information as required per local health authority.

### 7.2. Treatment Administration and Schedule

Tablets will be taken by mouth twice daily, in the morning (AM) and in the evening (PM), approximately 12 hours apart, with no food restrictions. To mitigate potential gastrointestinal (GI) adverse events, dose titration shall be implemented over a 5-day period (Table 14). At the Week 0 Visit, subjects will be dispensed a blister card with 10, 20, and 30 mg apremilast tablets for the dose titration. Subjects will be dispensed bottles with 30 mg apremilast tablets at designated visits.

**Table 14: Treatment Schema for Dose Titration at Baseline**

Week 0													
Day 1		Day 2		Day 3		Day 4		Day 5		Day 6			
AM	PM	AM	PM	AM	PM	AM	PM	AM	PM	AM	PM	AM	PM
10 mg	-	10 mg	10 mg	10 mg	20 mg	20 mg	20 mg	20 mg	30 mg				

Pictures of the blister card configurations are shown in Appendix S. Since dose modifications are not permissible in this study, if a subject develops severe renal impairment (creatinine clearance of less than 30 mL per minute estimated by the Cockcroft–Gault equation), interruption of study medication is required.

#### 7.2.1. Overdose

Overdose, as defined for this protocol, applies to protocol-required dosing of the IP(s) only. Therefore, for a drug to be subject to the overdose definition it must be *both required* and an *investigational drug*. In this study the only required and investigational drug is apremilast and there is no control arm drug, hence overdose definition will apply to only apremilast. Other required or optional non-study drugs intended for prophylaxis of certain side effects, etc, are excluded from this definition.

Overdose for this protocol, on a per dose basis, is defined as ingestion of 4 or more 30 mg apremilast tablets in any 24-hour period whether by accident or intentionally. On a schedule or frequency basis, an overdose is defined as dosing more than 4 times during any 24-hour period.

Adverse Events associated with an overdose must be collected on the Adverse Events page of the CRF (see Section 10) for all overdosed subjects, but the overdose itself is not considered an AE.

